1.3.1. Pharmacokinetics and Product Metabolism

Following administration of single oral doses of pomalidomide, the C_{max} occurs at 2 and 3 hours postdose. The systemic exposure (AUC) increases in an approximately dose proportional manner. Following multiple doses, pomalidomide has an accumulation ratio of 27% to 31%. Pomalidomide is a substrate for P-glycoprotein (P-gp) and is primarily metabolized in the liver by cytochrome 1A2 (CYP1A2) and CYP3A4. The drug is eliminated with a median plasma half-life of approximately 9.5 hours in healthy subjects and approximately 7.5 hours in patients with MM. The effect of CYP1A2 inhibitors, in the absence of a co-administered CYP3A4 and P-gp inhibitor, is unknown. However, co-administration of fluvoxamine (a strong CYP1A2 inhibitor) in the presence of ketoconazole (a strong CYP3A4 and P-gp inhibitor) to 12 healthy male subjects increased exposure (geometric mean AUC_{INF}) to pomalidomide by 146% compared to pomalidomide administered alone. Co-administration of pomalidomide with drugs that are CYP1A2 inducers has not been studied and may reduce pomalidomide exposure. Co-administration of ketoconazole (a strong CYP3A4 and P-gp inhibitor) in 16 healthy male subjects resulted in an increased exposure (geometric mean AUC_{INF}) to pomalidomide of 19% compared to pomalidomide administered alone. Co-administration of carbamazepine to 16 healthy male subjects decreased exposure (geometric mean AUC_{INF}) to pomalidomide by 21% compared to pomalidomide administered alone. Co-administration of multiple doses of 4 mg pomalidomide with 20 mg to 40 mg dexamethasone (a weak to moderate inducer of CYP3A4) to patients with MM had no effect on the PK of pomalidomide compared with pomalidomide administered alone. Pomalidomide does not inhibit or induce CYP450 enzymes or transporters in vitro.

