4.1.1. Inclusion Criteria for Open-label Sub-study Arm C (Phase 2b)

To be enrolled in the sub-study, each potential subject must meet all inclusion criteria defined in [Section 4.1](#). IN ADDITION the following criteria must be met:

Subject must have received pomalidomide in combination with dexamethasone (regimen must not have included other anti-cancer agents) as their most recent line of therapy and have:

- Achieved less than a partial response (<PR) following at least 112 days (4 x 28 day cycles) and are without evidence of progression disease (PD)
OR
- Disease progression following an initial confirmed response of MR or better to the combination (according to IMWG response criteria; [Rajkumar 2011](#))

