4.2. Exclusion Criteria

To be enrolled in the study, potential subjects must not have any of the following exclusion criteria:

Disease-Related

1. Primary refractory disease defined as nonresponsive in patients who have never achieved a minimal response or better with any therapy.
2. History of plasma cell leukemia, primary amyloidosis, POEMS syndrome within 12 months prior to first administration of study treatment.

Concurrent Conditions

3. Recent prior chemotherapy:
 - a. Alkylators (eg, melphalan, cyclophosphamide) and/or anthracyclines <21 days prior to first administration of study treatment.
 - b. High dose corticosteroids, IMiDs or proteasome inhibitors <14 days prior to first administration of study treatment.
 - c. Monoclonal antibody <14 days prior to first administration of study treatment.
4. Prior exposure to BTK inhibitors.
5. Prior exposure to pomalidomide (except Treatment Arm C).
6. History of serious hypersensitivity reactions to prior thalidomide, lenalidomide or pomalidomide.
7. History of other malignancies, except:
 - a. Malignancy treated with curative intent and with no known active disease present for ≥ 3 years before the first dose of study drug and felt to be at low risk for recurrence by treating physician.

- b. Adequately treated non-melanoma skin cancer or lentigo maligna without evidence of disease.
- c. Adequately treated carcinoma in situ without evidence of disease.
8. Peripheral neuropathy Grade ≥ 2 with pain at Screening.
9. Concurrent systemic immunosuppressant therapy (eg, cyclosporine A, tacrolimus, etc., or chronic administration of >20 mg/day of prednisone or equivalent) within 28 days of the first dose of study treatment.
10. Recent infection requiring systemic treatment that was completed <7 days before the first dose of study treatment and/or uncontrolled active systemic infection.
11. Unresolved toxicities from prior anti-cancer therapy, defined as having not resolved to [CTCAE \(version 4.03\)](#), Grade ≤ 1 or to the levels dictated in the inclusion/exclusion criteria with the exception of alopecia.
12. Known bleeding disorders (eg, von Willebrand's disease or hemophilia).
13. History of stroke or intracranial hemorrhage within 6 months prior to enrollment/randomization.

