7.6. Biomarker, Correlative and Special Studies

7.6.1. Pharmacokinetics

During treatment with ibrutinib or placebo in combination with pomalidomide and dexamethasone plasma concentrations of ibrutinib (PCI-32765), its metabolite PCI-45227 and pomalidomide will be determined using a validated analytical method on all patients in both Phase 1 and 2b. Other potential metabolites of ibrutinib may be explored. Plasma concentrations for 4- β -hydroxycholesterol, a marker of CYP3A induction, will be determined using a validated analytical method at time points specified in Table 7 below.

Refer to the Schedule of Assessments (Appendix 1) and the Pharmacokinetic Sample Schedule (Table 7).

Table 7: Pharmacokinetic Sample Schedule for Ibrutinib or Placebo and Pomalidomide with Dexamethasone

Cycle	Day	Predose ^b	Time after ibrutinib or placebo and pomalidomide with dexamethasone dosing ^a			
			1 hour (1h \pm 15 min)	2 hour (2 h \pm 15 min)	4 hour (4 h \pm 30 min)	6 hour (5 h to 8h)
Screening	NA	W				
1	15	X, W	X	X	X	X, W
2	15	X, W	X	X	X	X, W

W= Additional samples will be collected at Screening and following time-points in relation to dexamethasone dosing described in the table for the analysis of 4- β -hydroxycholesterol (CYP3A induction marker)

X = Pharmacokinetics timepoint for ibrutinib/placebo and pomalidomide

^{a.} Ibrutinib or placebo will be dosed at the same time as pomalidomide and dexamethasone.

^{b.} Samples for ibrutinib or placebo, pomalidomide, and 4- β -hydroxycholesterol should be collected approximately 24 (\pm 2 h) hours after previous study dose and approximately 30-60 minutes before ibrutinib or placebo, pomalidomide and dexamethasone administration.

Refer to the Laboratory Manual for instructions on collecting and processing PK samples. On the day of the sampling visit, the clinical staff will instruct the subject to not take ibrutinib or

placebo, pomalidomide or dexamethasone before arrival at the clinic. All three study drugs will be brought to the clinic and intake will be observed by clinic staff and time of last meal prior to administration of study treatment on Cycle 1 Day 15 and Cycle 2 Day 15 will be recorded. It is recommended that the clinical staff make reasonable effort with regards to subject dosing instructions during Cycles 1 and 2 to ensure appropriate collection times of the PK samples. The actual time (versus requested time) that each PK sample is drawn must be recorded using a 24 hour format.

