8.2. Screening Phase

Screening procedures will be performed up to 28 days before Cycle 1, Day 1. All subjects must first read, understand, and sign the IRB/IEC-approved ICF before any study-specific screening procedures are performed. After signing the ICF, screening and being deemed eligible for entry, subjects will be enrolled/randomized in the study.

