- ^w If abnormal, further testing should be performed as clinically appropriate. Testing will be performed at Screening and at EOT visits by local laboratory. Testing at additional time points may be performed at the Investigator's discretion.
- ^x Assessments pre- and postdose Ibrutinib or placebo and pomalidomide, see [Table 7](#). Ibrutinib will be administered in the treatment center on C1D15 and C2D15. Time of dose is to be recorded in the medical record for PK evaluation. For C1D15 and C2D15, record time of last meal prior to administration of study treatment.
- ^y Blood sample for 4- β -hydroxycholesterol will be drawn at Screening, pre-dose on Cycles 1 and 2 Day 15, and 6 hrs postdose on Cycles 1-2 Day 15.
- ^z An additional bone marrow aspirate (6 mL) to be collected for biomarker testing and submitted to a central lab at Screening, at the time of CR, and following confirmed PD (may be done at EOT or prior to the start of new anti-cancer therapy). Refer to [Section 7.5.7](#) for additional information.
- ^{aa} Biomarker serum CTX collections require 12 hour fasting prior to collection.
- ^{bb} T/B/NK must be collected predose (Phase 1 only).
- ^{cc} Hepatitis serologies including Hepatitis C antibody, Hepatitis B surface antigen, and Hepatitis B core antibody will be evaluated at Screening. If Hepatitis B core antibody, Hepatitis B surface antigen or Hepatitis C antibody is positive, then PCR to quantitate Hepatitis B/C must be performed and must be negative prior to randomization/enrollment.

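### The only pre-treatment sample for the CYP3A induction marker is taken at Screening, where the corticosteroid washout guarantees no steroid-free interval

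*Protocol*

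**What the plan says.** Protocol Section 7.6.1 introduces 4-beta-hydroxycholesterol as "a marker of CYP3A induction, will be determined using a validated analytical method at time points specified in Table 7 below". Table 7 ties its samples to dexamethasone dosing. Appendix 1, footnote y, states that blood for it "will be drawn at Screening, pre-dose on Cycles 1 and 2 Day 15, and 6 hrs postdose on Cycles 1-2 Day 15". The visit lists agree: the sample appears in Section 8.2.1 (Screening), 8.3.3 (Cycle 1 Day 15) and 8.3.6 (Cycle 2 Day 15), and is absent from 8.3.1 (Cycle 1 Day 1).

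On timing, Section 8.2 says "Screening procedures will be performed up to 28 days before Cycle 1, Day 1". No narrower window is set for this sample.

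On steroids before study entry, Section 4.2 has two limits, both counted back from the first dose:

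- Criterion 3b excludes "High dose corticosteroids, IMiDs or proteasome inhibitors <14 days prior to first administration of study treatment".
- Criterion 9, on concurrent immunosuppressants, includes "chronic administration of >20 mg/day of prednisone or equivalent) within 28 days of the first dose of study treatment".

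On the inducer, Section 1.3.1 describes "dexamethasone (a weak to moderate inducer of CYP3A4", and Appendix 5 lists glucocorticoids among the CYP3A4/5 inducers.

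On analysis, Protocol Section 10.5.6 does not mention the marker, and SAP Section 1 sends pharmacokinetic analyses to a separate document.

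**The concern.** An induction marker is read by comparing on-treatment values with a value taken before the inducer was given. The study inducer, weekly dexamethasone, starts on Cycle 1 Day 1. The next marker sample, pre-dose on Cycle 1 Day 15, follows the doses scheduled for Days 1 and 8, so Screening is the only value that can serve as baseline.

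The subjects have pre-treated myeloma, with progression on or within 60 days of finishing the last regimen (Section 4.1). Some may have been taking dexamethasone shortly before entry. If the Screening sample is drawn during or just after such treatment, it is already raised. A Day 15 to baseline ratio near 1 then cannot separate no induction from induction already present. Ibrutinib is cleared mainly by CYP3A4 (Section 1.2.2.1), and its pharmacokinetics with dexamethasone are a secondary objective. A false impression of no induction would therefore mislead the interpretation of exposure. The primary objectives and the response endpoints are not touched.

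**Working it through.** No sample size, power or error rate is attached to this marker, so there is no figure of the plan's own to reproduce. The check has three steps.

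**1. Guaranteed steroid-free interval.** Inputs: Screening window up to 28 days (Section 8.2); high-dose corticosteroids excluded only when taken fewer than 14 days before first dose (criterion 3b). For a sample drawn d days before first dose, the guaranteed interval off high-dose steroid is max(0, 14 − d) days.

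| Sample time | d | Guaranteed days off high-dose steroid |
|---|---|---|
| Start of Screening window | 28 | 0 |
| Day −14 | 14 | 0 |
| Day −7 | 7 | 7 |
| Cycle 1 Day 1 pre-dose | 0 | 14 |

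Criterion 9 changes this for one group. Chronic daily steroid above 20 mg prednisone equivalent is barred for 28 days before first dose, which spans the whole Screening window. It does not clearly reach intermittent anti-myeloma dexamethasone, which falls under 3b. If it did, the shorter 14-day corticosteroid limit would have little left to do.

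**2. Direction of the bias, with an illustration of size.** Let F be the true on-study fold-change from an uninduced baseline, and c the share of that induction already present in the baseline sample. Then

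observed fold = F / (1 + c(F − 1)).

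For F > 1 and c > 0 this is always below F. The documents give neither F nor c; the values below are assumptions, and zero carry-over is included. Brackets show the share of the true rise that is seen.

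| True F | c = 0 | c = 0.25 | c = 0.5 | c = 0.75 | c = 1 |
|---|---|---|---|---|---|
| 1.25 | 1.25 (100%) | 1.18 (71%) | 1.11 (44%) | 1.05 (21%) | 1.00 (0%) |
| 1.5 | 1.50 (100%) | 1.33 (67%) | 1.20 (40%) | 1.09 (18%) | 1.00 (0%) |
| 2.0 | 2.00 (100%) | 1.60 (60%) | 1.33 (33%) | 1.14 (14%) | 1.00 (0%) |

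Example: F = 1.5 and c = 0.5 give 1.5 / (1 + 0.5 × 0.5) = 1.5 / 1.25 = 1.20.

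**3. What a Cycle 1 Day 1 sample would gain.** Take the worst case that 3b allows: full induction when steroid stops, exactly 14 days before first dose. With an assumed marker half-life h in days, the residual share is c = 2^(−14/h). With F = 1.5:

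| Assumed h (days) | Residual c after 14 days | Observed fold from Cycle 1 Day 1 baseline |
|---|---|---|
| 3 | 4% | 1.47 |
| 7 | 25% | 1.33 |
| 14 | 50% | 1.20 |
| 21 | 63% | 1.14 |

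A Screening sample taken while the same subject was still fully induced (c = 1) would show 1.00. The later sample is better at every half-life, but is not free of carry-over when decay is slow.

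**The case against.** The strongest reply is that the harmed analysis is not written anywhere. Neither document defines a change from baseline for this marker, and the pharmacokinetic objective is served mainly by measured ibrutinib, metabolite and pomalidomide concentrations, which Screening timing does not affect. The separate pharmacokinetic document may already deal with it, since dates of prior anti-cancer treatment (Section 7.1.3) and recent medications (Section 7.1.5) are collected. This stands as a limit on importance. It does not remove the point: a pre-treatment sample of an induction marker has no evident use other than as baseline.

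A reader might go further in four ways, and the documents support none of them:

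- *That the on-study change is understated throughout.* It is understated only in subjects with residual induction at Screening. A CYP3A inhibitor in use at Screening could push the baseline the other way.
- *That about half the samples are affected.* Days −28 to −14 are 15 of 28 calendar days (54%), but that counts permitted days. Nothing says how many subjects are sampled then, or how many of those are on steroid.
- *That Arm C proves the problem.* Section 4.1.1 does require that "Subject must have received pomalidomide in combination with dexamethasone (regimen must not have included other anti-cancer agents) as their most recent line of therapy", but that fixes the last line of therapy, not the gap before Screening. SAP Section 6 says Phase 2 was not initiated, so Arm C has no subjects. For Phase 1, no criterion requires the last regimen to have contained a steroid.
- *That Section 1.3.1 settles the matter because dexamethasone had no pharmacokinetic effect.* That statement concerns pomalidomide, not ibrutinib.

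It is also fair to say that 14 days is not shown to be long enough, that 3b covers only high-dose steroid, and that chronic doses of 20 mg/day prednisone equivalent or less remain allowed even at Cycle 1 Day 1.

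**Conclusion.** The point holds in conditional form. The sole pre-treatment sample can be drawn with no guaranteed interval off high-dose steroid, against at least 14 days at Cycle 1 Day 1. In a subject whose Screening sample carries residual induction, a Day 15 versus baseline comparison would be biased toward no change. That direction follows from the schedule, the washout rule and the protocol's own classification of dexamethasone, provided Screening is used as baseline. The number of subjects affected and the size of the bias cannot be obtained from the documents; the tables above are illustrations on assumed inputs, and zero bias is within their range. This is a minor, inexpensive design improvement for one supporting pharmacokinetic marker. Only Phase 1 ran, with 11 treated subjects (SAP Section 1).

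**What to change.** In Table 7, Appendix 1 footnote y and its grid row, and Sections 8.2.1 and 8.3.1, take the baseline 4-beta-hydroxycholesterol sample at Cycle 1 Day 1 pre-dose instead of Screening, and name that value as baseline. Blood is already drawn pre-dose at that visit, so the cost is schedule wording, with no extra visit and no net extra sample. It reduces carry-over but may not eliminate it. With Phase 1 complete and Phase 2 not started, this change matters only if the schedule is used again.

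For subjects sampled only at Screening, the separate pharmacokinetic document should present the change from baseline by time since last corticosteroid, using the prior-treatment dates (Section 7.1.3) and medication records (Section 7.1.5). It should add a sensitivity summary limited to those with at least 14 days off steroid before the sample. The cost is fewer subjects in that summary, from at most 11, so a listing may be more useful than statistics. One gap remains: medications are recorded from consent or at least 14 days before first dose, so a non-myeloma steroid stopped earlier may not appear.

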Appendix 2. ECOG Status Scores

Status	Eastern Cooperative Oncology Group (ECOG) Performance Status**
0	Fully active, able to carry on all pre-disease performance without restriction.
1	Restricted in physically strenuous activity but ambulatory and able to carry out work of a light or sedentary nature, eg, light housework, office work.
2	Ambulatory and capable of all self-care, but unable to carry out any work activities. Up and about more than 50% of waking hours.
3	Capable of only limited self-care, confined to bed or chair more than 50% of waking hours.
4	Completely disabled. Cannot carry on any self-care. Totally confined to bed or chair.
5	Dead.

Available at: http://www.ecog.org/general/perf_stat.html. Accessed January 4, 2008.

Appendix 3. Cockcroft-Gault Formula for Estimating Creatinine Clearance

$$C_{cr} = \frac{(140 - \text{age}) \times \text{Body Weight (kg)}}{(\text{Serum creatinine mg/dL}) \times 72}$$

Note:

- Multiply by 0.85 for women
- Use with caution in cirrhosis and muscle wasting
- To convert μmol (micromoles)/L of creatinine to mg/dL, divide by 88.4.

Appendix 4. Lines of Therapy

According to the IMWG Consensus panel on uniform reporting criteria in clinical trials ([Rajkumar 2011](#)), a line of therapy consists of at least 1 or more cycles of a planned treatment regimen. This may consist of single-agent or combination therapy or a sequence of treatments administered in a planned manner. For example, a planned induction, followed by autologous stem cell transplant (ASCT) followed by maintenance is considered one line of therapy. A new line of therapy starts when a planned course is modified as a result of progression, relapse or toxicity or when a planned period of observation is interrupted by the need for additional treatment of the disease. Modification of drug doses or resuming therapy after holding will not be considered a new line of therapy provided that there was no evidence of progression of disease as defined in the “Response Criteria” section of this document.

Appendix 5. Inhibitors and Inducers of CYP3A

Inhibitors and inducers of CYP3A enzymes are defined as follows. Refer to [Section 6.1.2.1](#) on instructions for concomitant use of CYP3A inhibitors and inducers with ibrutinib. Further information can be found at the following website: <http://medicine.iupui.edu/clinpharm/ddis/main-table/>.

Inhibitors of CYP3A4/5	Inducers of CYP3A4/5
Strong inhibitors:	carbamazepine
indinavir	efavirenz
nelfinavir	nevirapine
ritonavir	barbiturates
clarithromycin	glucocorticoids
itraconazole	modafinil
ketoconazole	oxcarbazepine
nefazodone	phenobarbital
saquinavir	phenytoin
suboxone	pioglitazone
telithromycin	rifabutin
boceprevir	rifampin
cobicistat	St. John's Wort
mibefradil	troglitazone
posaconazole ^a	
telaprevir	
troleandomycin	
Moderate inhibitors:	
aprepitant	
erythromycin	
diltiazem	
fluconazole	
grapefruit juice	
Seville orange juice	
verapamil	
amiodarone	
amprenavir	
atazanavir	
ciprofloxacin	
crizotinib	
darunavir	
dronedarone	
fosamprenavir	
imatinib	
voriconazole ^a	
Weak inhibitors:	
cimetidine	
fluvoxamine	
All other inhibitors:	
Chloramphenicol	
delaviridine	
diethyl-dithiocarbamate	
gestodene	
mifepristone	
norfloxacin	
norflouxetine	
star fruit	

^a. Classification based on internal data.

Appendix 6. QT Drugs by Risk Group

QT-prolonging drugs grouped by risk of torsades, possible risk of torsades, and conditional risk of torsades are included in the tables below.

Risk for Torsades de Pointes and/or QT prolongation

Drugs that are generally accepted by the QTdrugs.org Advisory Board of the Arizona CERT to have a risk of causing torsades de pointes are listed below.

Generic Name	Class/Clinical Use	Comments
Amiodarone	Anti-arrhythmic / abnormal heart rhythm	Females>Males, TdP risk regarded as low
Arsenic trioxide	Anti-cancer / Leukemia	
Astemizole	Antihistamine / Allergic rhinitis	No Longer available in U.S.
Bepriidil	Anti-anginal / heart pain	Females>Males
Chloroquine	Anti-malarial / malaria infection	
Chlorpromazine	Anti-psychotic/ Anti-emetic / schizophrenia/ nausea	
Cisapride	GI stimulant / heartburn	Restricted availability; Females>Males.
Clarithromycin	Antibiotic / bacterial infection	
Disopyramide	Anti-arrhythmic / abnormal heart rhythm	Females>Males
Dofetilide	Anti-arrhythmic / abnormal heart rhythm	
Domperidone	Anti-nausea / nausea	Not available in the U.S.
Droperidol	Sedative; Anti-nausea / anesthesia adjunct, nausea	
Erythromycin	Antibiotic; GI stimulant / bacterial infection; increase GI motility	Females>Males
Halofantrine	Anti-malarial / malaria infection	Females>Males
Haloperidol	Anti-psychotic / schizophrenia, agitation	When given intravenously (IV) or at higher-than- recommended doses, risk of sudden death, QT prolongation and torsades increases.
Ibutilide	Anti-arrhythmic / abnormal heart rhythm	Females>Males
Levomethadyl	Opiate agonist / pain control, narcotic dependence	
Mesoridazine	Anti-psychotic / schizophrenia	
Methadone	Opiate agonist / pain control, narcotic dependence	Females>Males
Moxifloxacin	Antibiotic / bacterial infection	
Pentamidine	Anti-infective / pneumocystis pneumonia	Females>Males

Generic Name	Class/Clinical Use	Comments
Pimozide	Anti-psychotic / Tourette's tics	Females>Males
Probucol	Antilipemic / Hypercholesterolemia	No longer available in U.S.
Procainamide	Anti-arrhythmic / abnormal heart rhythm	
Quinidine	Anti-arrhythmic / abnormal heart rhythm	Females>Males
Sotalol	Anti-arrhythmic / abnormal heart rhythm	Females>Males
Sparfloxacin	Antibiotic / bacterial infection	
Terfenadine	Antihistamine / Allergic rhinitis	No longer available in U.S.
Thioridazine	Anti-psychotic / schizophrenia	

Revised: 06/06/2011.

Printed: 02/24/2012.

Source: www.QTdrugs.org.

Possible Risk for Torsades de Pointes and/or QT Prolongation

Drugs that in some reports have been associated with torsades de pointes and/or QT prolongation but at this time lack substantial evidence for causing torsades de pointes are listed below.

Generic Name	Class/Clinical Use	Comments
Alfuzosin	Alpha 1-blocker / Benign prostatic hyperplasia	
Amantadine	Dopaminergic/Anti-viral / Anti-infective/ Parkinson's Disease	
Atazanavir	Protease inhibitor / HIV	
Azithromycin	Antibiotic / bacterial infection	
Chloral hydrate	Sedative / sedation/ insomnia	
Clozapine	Anti-psychotic / schizophrenia	
Dolasetron	Anti-nausea / nausea, vomiting	
Dronedarone	Anti-arrhythmic / Atrial Fibrillation	
Escitalopram	Anti-depressant / Major depression/ Anxiety disorders	
Felbamate	Anti-convulsant / seizure	
Flecainide	Anti-arrhythmic / abnormal heart rhythm	
Foscarnet	Anti-viral / HIV infection	
Fosphenytoin	Anti-convulsant / seizure	
Gatifloxacin	Antibiotic / bacterial infection	
Gemifloxacin	Antibiotic / bacterial infection	
Granisetron	Anti-nausea / nausea and vomiting	
Indapamide	Diuretic / stimulate urine & salt loss	

Generic Name	Class/Clinical Use	Comments
Isradipine	Anti-hypertensive / high blood pressure	
Lapatinib	Anti-cancer / breast cancer, metastatic	
Levofloxacin	Antibiotic / bacterial infection	
Lithium	Anti-mania / bipolar disorder	
Moexipril/HCTZ	Anti-hypertensive / high blood pressure	
Nicardipine	Anti-hypertensive / high blood pressure	
Nilotinib	Anti-cancer / Leukemia	
Octreotide	Endocrine / acromegaly, carcinoid diarrhea	
Ofloxacin	Antibiotic / bacterial infection	
Ondansetron	Anti-emetic / nausea and vomiting	
Oxytocin	Oxytocic / Labor stimulation	
Paliperidone	Antipsychotic, atypical / Schizophrenia	
Perflutren lipid microspheres	Imaging contrast agent / Echocardiography	
Quetiapine	Anti-psychotic / schizophrenia	
Ranolazine	Anti-anginal / chronic angina	
Risperidone	Anti-psychotic / schizophrenia	
Roxithromycin*	Antibiotic / bacterial infection	*not available in the United States
Sertindole	Antipsychotic, atypical / Anxiety, Schizophrenia	
Sertindole	Antipsychotic, atypical / Anxiety, Schizophrenia	
Sunitinib	Anti-cancer / RCC, GIST	
Tacrolimus	Immunosuppressant / Immune suppression	
Tamoxifen	Anti-cancer / breast cancer	
Telithromycin	Antibiotic / bacterial infection	
Tizanidine	Muscle relaxant /	
Vardenafil	phosphodiesterase inhibitor / vasodilator	
Venlafaxine	Anti-depressant / depression	
Voriconazole	Anti-fungal / anti-fungal	
Ziprasidone	Anti-psychotic / schizophrenia	

Revised: 12/21/2011.
Printed: 02/24/2012.
Source: www.QTdrugs.org.

Conditional Risk for Torsades de Pointes and/or QT Prolongation

Drugs that, in some reports, have been weakly associated with torsades de pointes and/or QT prolongation but that are unlikely to be a risk for torsades de pointes when used in usual recommended dosages and in subjects without other risk factors (e.g., concomitant QT prolonging drugs, bradycardia, electrolyte disturbances, congenital long QT syndrome, concomitant drugs that inhibit metabolism) are listed below.

Generic Name	Class/Clinical Use	Comments
Amitriptyline	Tricyclic Antidepressant / depression	
Ciprofloxacin	Antibiotic / bacterial infection	
Citalopram	Anti-depressant / depression	
Clomipramine	Tricyclic Antidepressant / depression	
Desipramine	Tricyclic Antidepressant / depression	
Diphenhydramine	Antihistamine / Allergic rhinitis, insomnia	
Doxepin	Tricyclic Antidepressant / depression	
Fluconazole	Anti-fungal / fungal infection	
Fluoxetine	Anti-depressant / depression	
Galantamine	Cholinesterase inhibitor / Dementia, Alzheimer's	
Imipramine	Tricyclic Antidepressant / depression	
Itraconazole	Anti-fungal / fungal infection	
Ketoconazole	Anti-fungal / fungal infection	
Nortriptyline	Tricyclic Antidepressant / depression	
Paroxetine	Anti-depressant / depression	
Protriptyline	Tricyclic Antidepressant / depression	
Ritonavir	Protease inhibitor / HIV	
Sertraline	Anti-depressant / depression	
Solifenacin	muscarinic receptor antagonist / treatment of overactive bladder	
Trazodone	Anti-depressant / Depression, insomnia	
Trimethoprim-Sulfa	Antibiotic / bacterial infection	
Trimipramine	Tricyclic Antidepressant / depression	

Revised: 03/30/2010.

Printed: 05/25/2011.

Source: www.QTdrugs.org.

Drugs on the QT Drug Lists are reviewed on an ongoing basis to assure the evidence is still appropriate for their placement on their respective list.

**Appendix 7. International Myeloma Working Group Response Criteria
(Rajkumar 2011)**

IMWG Response Criteria	
CATEGORY	RESPONSE CRITERIA ^a
Stringent complete response (sCR)	CR as defined below plus all of the following: 
 • Normal serum FLC ratio • Absence of clonal cells in bone marrow by IHC or immunofluorescence ^b
Complete response (CR)	
 • Negative immunofixation of the serum and urine • <5% plasma cells in bone marrow • Disappearance of any soft tissue plasmacytomas • If at on study, the only measurable non-bone marrow parameter was FLC, normalization of FLC ratio
Very good partial response (VGPR)	
 • PR as defined below plus all of the following: • Serum and urine M-component detectable by immunofixation but not on electrophoresis or • If at on study, serum measurable, $\geq 90\%$ or greater reduction in serum M-component plus urine M-component <100 mg per 24 h
Partial Response (PR)	
 • One of the following: 
 ▪ If at on study, serum and urine measurable, a $\geq 50\%$ reduction of serum M-protein and reduction in 24-h urinary M-protein by $\geq 90\%$ or to <200 mg per 24 h ▪ If at on study, only serum measurable (but urine not), a $\geq 50\%$ reduction of serum M-protein ▪ If at on study, urine measurable (but serum not), a reduction in 24-h urinary M-protein by $\geq 90\%$ or to <200 mg per 24 h • In addition to the above criteria, if a plasmacytoma present at baseline, $\geq 50\%$ reduction in the size of soft tissue plasmacytomas is also required
Minimal Response (MR)	
 • $\geq 25\%$ but $\leq 49\%$ reduction of serum M-protein and reduction in 24h urine M-protein by 50-89% • In addition to the above criteria, if a plasmacytoma present at baseline, 25-49% reduction in the size of soft tissue plasmacytomas is also required • No increase in size or number of lytic bone lesions (development of compression fracture does not exclude response)
Stable disease (SD)	Not meeting criteria for CR, VGPR, PR, MR or progressive disease

IMWG Response Criteria	
CATEGORY	RESPONSE CRITERIA ^a
Progressive disease (PD)	
Any one or more of the following:
 
 • Increase of 25% from lowest value in ^d: 
 ▪ Serum M-component (absolute increase must be ≥ 0.5 g/dL)^c ▪ Serum M-component increase ≥ 1 g/dL, if starting M component was ≥ 5 g/dL ▪ Urine M-component (absolute increase must be ≥ 200 mg/24 h) ^c 
Or any one or more of the following felt related to the underlying clonal plasma cell proliferative disorder
 
 ▪ Development of new soft tissue plasmacytomas or bone lesions ▪ Hypercalcemia (corrected serum calcium ≥ 11.5 mg/dL)

^a All response categories require two consecutive assessments made at any time before the institution of any new therapy; CR and PR, MR and SD categories also require no known evidence of progressive or new bone lesions if radiographic studies were performed. Radiographic studies are not required to satisfy these response requirements. Bone marrow assessments need not be confirmed.

^b Presence/absence of clonal cells is based upon the k/λ ratio. An abnormal k/λ ratio by IHC and/or immunofluorescence requires a minimum of 100 plasma cells for analysis. An abnormal ratio reflecting presence of an abnormal clone is k/λ of $>4:1$ or $<1:2$.

^c Positive immunofixation alone in a subject previously classified as CR will not be considered progression.

^d In the case where a value is felt to be a spurious result per physician discretion (for example, a possible lab error), that value will not be considered when determining the lowest value.

Confirmation of Response Categories

In order to be classified as a hematologic response, confirmation of serum monoclonal protein, and urine monoclonal protein (when primary determinant of response) results must be made by verification on two consecutive determinations. Confirmation assessments may be performed at any time after the initial assessment.

- Bone marrow aspirate/biopsy is **only** required to document CR. However, a second confirmatory bone marrow is not required to confirm response in any case.
- Radiographic studies are not required to satisfy these response requirements; however, if radiographic studies were performed there should be no evidence of progressive or new bone lesions.

Measurable disease

- Serum M-protein ≥ 1 g/dL
- Urine M-protein ≥ 200 mg/24 h

For Phase 2b the primary efficacy evaluations are based on IRC assessment. The IRC assessment will incorporate assessments from the central laboratory and additional assessments (as indicated) based upon evaluations outlined in [Section 7.5](#) Details regarding the IRC evaluation for response and progression will be outlined in a separate charter.

